1. PROTOCOL SUMMARY

1.1. Synopsis

Brief Title

A Phase 1 Radiolabel Pharmacokinetics, Excretion, Mass Balance and Metabolism Study of [¹⁴C]PF-07265803.

Rationale

The purpose of this Phase 1 study is to assess the pharmacokinetics, excretion, mass balance and metabolism of PF-07265803 (formerly known as known as ARRY-371797) in healthy adult male participants. Only males will be included in this study given the use of radiolabeled substance and the desire to enroll a homogeneous population given the small sample size of this study.

Administration of the investigational product, [¹⁴C]PF-07265803 in this study will be via the oral route to reflect the intended route of administration in the treatment of lamin A/C gene mutation (*LMNA*)-related DCM. PF-07265803 will be administered as an extemporaneously prepared liquid formulation in this study. In order to limit the confounding of absorption, [¹⁴C]PF-07265803 will be administered following an overnight fast of at least 10 hours.

Objectives and Endpoints

Objectives	Endpoints
Primary: To characterize rate and extent of excretion of total radioactivity in urine and feces, following a single oral dose of [¹⁴ C]PF-07265803 administered to healthy adult male participants.	Primary: Mass Balance: cumulative recovery of urinary, fecal, and total excretion of radioactivity over time expressed as percentage of total radioactive dose administered.
To characterize metabolic profile and identify circulating and excreted metabolites following administration of a single oral dose of [¹⁴ C]PF-07265803 to healthy adult male participants.	Metabolic profiling/identification and determination of relative abundance of PF-07265803 and the metabolites of PF-07265803 in plasma, urine, and feces.
Secondary: To quantify plasma concentrations and pharmacokinetic parameters of PF-07265803, its known circulating metabolites (PF-07327859, PF-07327860, PF-07327890) and total radioactivity in plasma following administration of a single oral dose of [¹⁴ C]PF-07265803 to healthy adult male participants.	Secondary: Pharmacokinetics parameter AUC _{last} , AUC _{inf} , CL/F, V _z /F, C _{max} , T _{max} , and t _{1/2} to describe single dose PK of: PF-07265803 and where appropriate PF-07327859, PF-07327860, PF-07327890. Total radioactivity in plasma; PF-07265803, PF-07327859, PF-07327860 and PF-07327890 concentrations in plasma.
To evaluate safety and tolerability of a single oral dose of [¹⁴ C]PF-07265803 administered to healthy adult male participants.	Safety endpoints including physical examinations, adverse events, clinical laboratory measurements, vital signs and ECG.

Overall Design

This is a Phase 1, open-label, single-period, single-center, non-randomized study in healthy adult male participants.

Brief Summary

In this study, mass balance and metabolism of 400 mg PF-07265803 containing 100 μ Ci [^{14}C]PF-07265803 will be assessed. Healthy participants will be screened up to 28 days prior to dosing to determine eligibility.

Number of Participants

Approximately 6 participants will be enrolled to study intervention.

Note: "Enrolled" means a participant's, or his or her legally authorized representative's, agreement to participate in a clinical study following completion of the informed consent process and screening. A participant will be considered enrolled if the informed consent is not withdrawn prior to participating in any study activity after screening. Potential participants who are screened for the purpose of determining eligibility for the study, but do not participate in the study, are not considered enrolled, unless otherwise specified by the protocol.

Intervention Groups and Duration

The duration of this non-randomized Phase 1, open-label, single-center, single-dose study is approximately 7 days, with a 30-day safety follow up. The maximum period of confinement is expected to be 14 days. The minimum period of confinement is expected to be 3 days.

Data Monitoring Committee or Other Independent Oversight Committee: No

This study will not use a DMC or IOC.

Statistical Methods

There will be no formal hypothesis testing in this study. The sample size of 6 participants, for this study, was not based on empirical data or hypothesis testing criteria. The sample size has been selected to ensure that at least 4 participants provide evaluable data; with intent not to replace participants who prematurely withdraw (or offer non-evaluable or partially evaluable data).

1.2. Schema

Not applicable.

1.3. Schedule of Activities

The SoA table provides an overview of the protocol visits and procedures. Refer to the **STUDY ASSESSMENTS AND PROCEDURES** section of the protocol for detailed information on each procedure and assessment required for compliance with the protocol.

The investigator may schedule visits (unplanned visits) in addition to those listed in the SoA table, in order to conduct evaluations or assessments required to protect the well-being of the participant.

Visit Identifier Abbreviations used in this table may be found in 10.9.	Screening	Period 1							Follow-Up	Early Termination/ Discontinuation
Days Relative to Day 1	Day -28 to Day -2	Day -1	Day 1	Day 2	Day 3	Day 4	Day 5	Day 6-14	28-35 Days ^b	
Informed consent	X									
CRU confinement ^a		X	X	X	X	X	X	X ^a		
Inclusion/exclusion criteria	X	X								
Medical/medication history	X	X								
Physical exam ^b		X						X ^c		X
Safety laboratory ⁱ	X	X						X ^c		X
Demography	X									
Height and Weight	X									
Urine drug/alcohol/cotinine testing ^k	X	X								
12-Lead ECG	X		X ^{g,j}					X ^c		X
Blood pressure and pulse rate	X		X ^{h,j}					X ^c		X
Contraception check									X	
HIV, HBsAg, HCVAb	X									
COVID-19 CRU Internal Procedure ^d	X	X	X	X	X	X	X	X ^c		X
Study intervention administration			X							
Standard Meals ^e		X	X	X	X	X	X			
Spot Collection for Urinalysis (and Microscopy, if needed)	X	X						X ^c		X
Retained Research Sample for Genetics (Prep D1) ^f			X							
CRU discharge								X ^a		
Serious and nonserious AE monitoring	X	X	X	X	X	X	X	X	X	X

PFIZER CONFIDENTIAL

Visit Identifier Abbreviations used in this table may be found in 10.9 .	Screening	Period 1						Follow-Up	Early Termination/ Discontinuation	
Days Relative to Day 1	Day -28 to Day -2	Day -1	Day 1	Day 2	Day 3	Day 4	Day 5	Day 6-14	28-35 Days ^b	

- a. Inpatient stay must be extended until >90% radioactive dose administered has been recovered or <1% is excreted in total (urine and feces) in any 24H period for two consecutive days. Maximum confinement will be 14 days.
- b. Complete physical examination will be conducted at Day -1 (Period 1); otherwise brief physical exam envisioned for findings during previous PE or new/open AEs, at Investigator discretion. Follow-up over the phone may be conducted if no new/open AE's at Investigators discretion.
- c. Procedures to be completed at time of discharge (approximately 144 hours post dose) only, with clinical laboratory tests conducted only after criteria for discharge (footnote "a") are satisfied
- d. Assessments for COVID-19 infection will be done per CRU standards for testing and those described in Section [8.2.5](#)
- e. Starting at enrollment, meals to be served, at clock times matching approximately 0H, 4H, and 9H relative to dosing on Day 1. No meal administered on Day 1 0 h in accordance with the fasted window. To help assure regularity in bowel movements, nutritional composition should contain at least 15 g of fiber per 1000 kcal or fiber capsules containing the equivalent amount of fiber may be administered daily (beginning at least 8 hr after dosing).
- f. Prep D1 Retained Research Samples for Genetics: If not collected on the designated collection day, collect at the next available time point when biospecimens are being collected in conjunction with a participant visit. Sample should be collected prior to dose.
- g. ECG assessment will occur prior to dosing (approximately 1 hour).
- h. Pre-dose vital sign measurements. Predose (approximately 1 hour) vital sign measurements on Day 1.
- i. Safety laboratories consistent with those described in Section [10.2](#)
- j. ECG and vital signs assessment for eligibility may be considered at both screening and Day 1 visit (predose).
- k. Urine drug screen and cotinine conducted at screening and check-in, and urine alcohol conducted at check-in only.

Visit Identifier	Period 1															
Study Day	1						2		3	4	5	6	Early Termination/ Discontinuation			
Hours Before/After Dose	0 ^a	0.5	1	2	3	4	6	9	12	24	36	48	72	96	120	
Study intervention administration	X															
PK blood sampling	X	X	X	X	X	X	X	X	X	X	X	X	X	X	X	
Radioactivity and metabolite ID in blood	X	X	X	X	X	X	X	X	X	X	X	X	X	X	X	
Interval collection for radioactivity and metabolite ID in urine ^b	X	→	→	→	→	→	X	→	X	X	→	X	X	X	X	
Interval collection for radioactivity and metabolite ID in feces ^c	X	→	→	→	→	→	→	→	X	X	→	X	X	X	X	
Emesis Collection for Radioactivity Measurement, if Occurs	X	→	→	→	→	→	→	→	→	X						

- a. Predose sample collection
- b. “Blank” spot urine sample to be collected anytime predose (Day 1) and postdose in intervals of 0-6H, 6-12H, 12-24H, 24-48H, 48-72H, 72-96H, and each subsequent 24H interval up to discharge.
- c. “Blank” fecal sample to be collected prior to dosing but post admission to CRU and in intervals of each 24H period post dose up to discharge

2. INTRODUCTION

PF-07265803 (formerly known as known as ARRY-371797) is a potent and selective, oral small molecule inhibitor of the α isoform of p38 MAPK. Mutations in the *LMNA* gene encoding nuclear lamina components cause nuclear envelope dysfunction leading to altered nuclear activity, impaired structural dynamics and aberrant cell signaling including activation of p38 α MAPK signaling pathways. Structural alterations in the nuclear envelope and connected cytoskeleton resulting from *LMNA* mutations make cardiomyocytes highly susceptible to damage even by physiological mechanical stress, leading to a disease specific maladaptive activation of the p38 α MAPK. Up-regulation of p38 MAPK has been observed in the hearts of animal models and adult patients with *LMNA*-related DCM compared to wild-type/healthy individuals. Inhibition of p38 MAPK in this disease setting may halt aberrant apoptosis and cardiac remodeling resulting in improved cardiac function.

2.1. Study Rationale

The purpose of this Phase 1 study is to assess the pharmacokinetics, excretion, mass balance and metabolism of PF-07265803 (formerly known as ARRY-37197) in healthy adult male participants. Only males will be included in this study given the use of radiolabeled substance and the desire to enroll a homogeneous population given the small sample size of this study.

Administration of the investigational product, [^{14}C]PF-07265803 in this study will be via the oral route to reflect the intended route of administration in the treatment of lamin A/C gene mutation (*LMNA*)-related DCM. PF-07265803 will be administered as an extemporaneously prepared liquid formulation in this study. In order to limit the confounding of absorption, [^{14}C]PF-07265803 will be administered following an overnight fast of at least 10 hours.

2.2. Background

In the completed Phase 2 study ARRAY-797-231, treatment with PF-07265803 resulted in rapid (<4 weeks), sustained increases in functional capacity in participants with *LMNA*-related DCM. Improvements on the 6MWT compared to baseline, the primary endpoint, were mirrored by favorable changes in NT-proBNP levels, LVEF, and RV fractional area. PF-07265803 was generally well tolerated. The AEs for most participants were mild to moderate, and only 1 participant discontinued the study because of a treatment-related AE. Based on these clinical data, inhibition of p38 MAPK with the selective p38 inhibitor PF-07265803 may provide a novel therapeutic approach and has the potential to fill an unmet medical need for the treatment of symptomatic *LMNA*-related DCM and is being evaluated in the Phase 3 study, C4411002.

2.2.1. Nonclinical Studies with PF-07265803

Detailed information regarding nonclinical studies of PF-07265803 is presented in the IB.

2.2.2. Nonclinical Pharmacology

Numerous in vitro and in vivo studies were performed to evaluate and confirm the ability of PF-07265803 to interact with its intended target, p38 MAPK. In enzyme studies, PF-07265803 inhibits p38a with a half-maximal inhibitory concentration (IC₅₀) of 8.2 nM. In cellular studies, PF-07265803 is a potent inhibitor of p38-mediated downstream phosphorylation of HSP27 in HeLa cells with an IC₅₀ of 17 nM. This compound has demonstrated little to no activity against over 201 enzymes, receptors, channels, and transporters.

Two in vivo murine models of *LMNA*-related DCM have allowed exploration of pathophysiologic mechanisms of disease progression and novel therapies for these conditions. In vivo studies have demonstrated that p38 MAPK is activated in murine models of *LMNA*-related DCM and that this activation of p38 MAPK precedes the development of cardiac dysfunction. PF-07265803 has been tested in the homozygous *LMNA* H222P model of EDMD with cardiomyopathy (EDMD2, MIM:181350) and in the homozygous *LMNA* N195K model of *LMNA*-related DCM, one of the original *LMNA* mutations linked to familial DCM with conduction defects¹. These 2 nonclinical models bracket the spectrum of phenotypes (EDMD2: cardiac and skeletal muscle disease and DCM: cardiac disease only). Results from these studies confirm that treatment with PF-07265803 improves cardiac structure and function and reduces myocardial apoptosis.

2.2.3. Nonclinical Pharmacokinetics and Metabolism

Multiple Phase 1 enzymes (CYPs, FMOs, amidases, and esterases) are involved in the metabolism of PF-07265803.

In vitro experiments indicated that PF-07265803 has moderate membrane permeability and may be a substrate for active efflux. PF-07265803 was moderately, but reversibly, bound to plasma proteins in vitro across mouse, monkey, and human plasma, as was AR00420643, the principal metabolite in vivo. PF-07265803 was predicted to have moderate-to-good stability in humans with respect to hepatic metabolism. The principal metabolite in vivo, AR00420643, is formed in in vitro incubations with liver microsomes, hepatocytes, plasma, or blood.

CYP-mediated metabolism was primarily by CYP3A4 and CYP2D6; however, these enzymes do not generate the principal metabolite in vivo. In vivo, other Phase 1 enzymes (FMOs, amidases, and esterases) are involved in the metabolism of PF-07265803, with the major mechanism of clearance thought to be through an unidentified hydrolase enzyme. PF-07265803 and its metabolites were weak inhibitors of 5 major CYP isoforms in vitro (CYP2C19, CYP2C9, CYP1A2, CYP2D6, CYP3A4). PF-07265803 is a weak time-dependent inhibitor of CYP3A4. In in vitro studies in human hepatocytes, PF-07265803 and its metabolites are inducers of CYP3A, while only metabolites AR00420643 and AR00428028 induce CYP2B6. Based on potential for mixed induction/inhibition of CYP3A4, the net effect of PF-07265803 interaction with drugs that are identified as CYP3A4 cannot be predicted. PF-07265803 has the potential to inhibit P-gp, but overall data suggest that PF-07265803 is not a very potent P-gp inhibitor.

PF-07265803 is not a substrate or inhibitor of recombinant MAO-A or MAO-B. AR00420643 is a principal metabolite from in vitro incubations with liver microsomes, hepatocytes, plasma, or blood. Other, less abundant, metabolites that are found in vitro or in vivo are a result of oxidative metabolism. No glucuronide conjugates were detected in hepatocyte incubations

2.2.4. Nonclinical Safety

Preclinical toxicological studies have indicated that PF-07265803 was well-tolerated at multiple doses of up to 100 mg/kg BID in rats and monkeys, with GI side effects and minimal clinical pathology changes. Associated histopathology changes were reversible in monkeys treated with doses of up to 100 mg/kg BID for 28 days. Histopathology findings in rats receiving PF-07265803 for 28 days were partially reversible with respect to severity and incidence at the 100 mg/kg BID (200 mg/kg/day) dose level. In the chronic dosing studies for up to 6 months in the rat and 9 months in the monkey at doses up to 30 mg/kg BID, there were no significant adverse histopathology findings. In general, administration of PF-07265803 at doses of up to 30 mg/kg BID was tolerated in-life in rats and monkeys in chronic safety studies. Administration of PF-07265803 to rats for up to 3 months was associated with microscopic findings of skeletal muscle fiber changes, with no effects on clinical chemistry. These skeletal muscle changes were reversible after dosing cessation and with continued dosing for up to 6 months. Evidence of gastric irritation and increased gastric fluid secretion was observed in rats after a single oral dose of 100 mg/kg of PF-07265803. After treatment with PF-07265803 for multiple days, evidence of changes in stool consistency, ranging from loose stools to diarrhea was observed in monkeys. The GI disturbances were mild to moderate in the lower dose groups. In most dose groups, these GI effects resolved within 28 days after discontinuation of treatment with PF-07265803.

2.2.5. Clinical Overview

PF-07265803 is currently undergoing investigation in a Phase 3, multinational, randomized, placebo controlled study in which patients with symptomatic *LMNA*-related DCM (planned N=160) are randomized 1:1 to receive PF-07265803 400 mg BID or placebo.

PF-07265803 has been investigated in 12 completed clinical studies including a Phase 2 study in patients with *LMNA*-related DCM and long-term rollover extension to the Phase 2. In addition, 5 studies (one Phase 1b and four Phase 2) in patients with painful inflammatory conditions have been completed as well as five Phase 1 studies in healthy subjects.

In 5 clinical studies in healthy subjects, PF-07265803 demonstrated an acceptable safety profile when administered at single doses up to 900 mg QD, up to 400 mg/day for 14 days and up to 2000 mg/day for 7 days. In these studies, the most commonly reported AEs in subjects receiving PF-07265803 were dizziness, headache, diarrhea, nausea and acne; the incidence of these AEs was not clearly related to the PF-07265803 dose or to the duration of exposure.

Detailed information regarding clinical studies of PF-07265803 is presented in the IB.

2.3. Benefit/Risk Assessment

PF-07265803 as a single dose is not expected to provide any clinical benefit to healthy participants. This study is designed primarily to generate safety, tolerability, and pharmacokinetic data for further clinical development.

More detailed information about the known and expected benefits and risks and reasonably expected adverse events of PF-07265803 may be found in the Investigator's Brochure, which is the SRSD for this study.

2.3.1. Risk Assessment

Potential Risk of Clinical Significance	Summary of Data/Rationale for Risk	Mitigation Strategy
Study Intervention(s) PF-07265803		
An identified risk associated with this study intervention is stomatitis. It is a common ($\geq 1/100$ to $<1/10$) event in the protocol population.	The potential risks are based on adverse events reported in early studies of PF-07265803 (ARRY-371797).	AEs will be monitored on an ongoing basis. Instructions for managing potential cases of stomatitis can be discussed with the sponsor.
First time clinical administration of [¹⁴ C]PF-07265803	
Single oral doses up to 900 mg of PF-07265803 observed to be well tolerated; single, oral dose of PF-07265803 in this study (400 mg) represents is >2-fold lowerThe maximum whole-body exposure of humans to radioactivity from a 100 μCi (3.7 MBq) PO dose of [¹⁴C] PF-07265803PF-07265803, which was predicted using this rodent tissue distribution data was 0.39 mrem. This was approximately 0.013% of the 3 to 5 rem limit specified for whole-body exposure by the Code of Federal Regulations. The predicted exposure of the blood-forming organs, gonads and 29 other tissues to radioactivity from an PO dose of 100 μCi of [¹⁴C]PF-07265803 to humans were each less than 1.0% of the 3 to 5 rem limits specified by the Code of Federal Regulations.	
Administration of PF-07265803 will occur in an inpatient setting under close supervisionClear communication via ICD of negligible risk with the [¹⁴C]PF-07265803 doses administered relative to previously administered oral doses.

PFIZER CONFIDENTIAL

2.3.2. Benefit Assessment

The participants in this study are not expected to obtain any specific benefit beyond contributing to the process of developing new therapies in an area of unmet need. They will receive close monitoring of their safety via study procedures undertaken (eg. Physical examination, 12-lead ECGs, vital signs) which will occur as outlined in this protocol.

2.3.3. Overall Benefit/Risk Conclusion

Taking into account the measures to minimize risk to study participants, the potential risks identified in association with PF-07265803 are justified by the anticipated benefits that may be afforded to participants with *LMNA*-related DCM. The overall benefit:risk profile for PF-07265803 supports continued clinical development and the conduct of this study.

3. OBJECTIVES AND ENDPOINTS

Objectives	Endpoints
Primary: To characterize rate and extent of excretion of total radioactivity in urine and feces, following a single oral dose of [¹⁴ C]PF-07265803 administered to healthy adult male participants.	Primary: Mass Balance: cumulative recovery of urinary, fecal, and total excretion of radioactivity over time expressed as percentage of total radioactive dose administered.
To characterize metabolic profile and identify circulating and excreted metabolites following administration of a single oral dose of [¹⁴ C]PF-07265803 to healthy adult male participants.	Metabolic profiling/identification and determination of relative abundance of PF-07265803 and the metabolites of PF-07265803 in plasma, urine, and feces.
Secondary: To quantify plasma concentrations and pharmacokinetic parameters of PF-07265803, its known circulating metabolites (PF-07327859, PF-07327860, PF-07327890) and total radioactivity in plasma following administration of a single oral dose of [¹⁴ C]PF-07265803 to healthy adult male participants.	Secondary: Pharmacokinetic parameters AUC _{last} , AUC _{inf} , CL/F, V _z /F, C _{max} , T _{max} , and t _{1/2} to describe single dose PK of: PF-07265803 and where appropriate PF-07327859, PF-07327860, PF-07327890. Total radioactivity in plasma; PF-07265803, PF-07327859, PF-07327860 and PF-07327890 concentrations in plasma.
To evaluate safety and tolerability of a single oral dose of [¹⁴ C]PF-07265803 administered to healthy adult male participants.	Safety endpoints including physical examinations, adverse events, clinical laboratory measurements, vital signs and ECG.

4. STUDY DESIGN

4.1. Overall Design

This is a Phase 1, open-label, single-period, single-center, non-randomized single oral dose study administering a liquid formulation with 400 mg of PF-07265803 containing 100 µCi of [¹⁴C]PF-07265803 to healthy male participants. Participants will be screened for participation in this study within 28 days before dosing on Day 1 to confirm that they meet the inclusion/exclusion criteria specified in [Section 5.1](#).

The duration of this non-randomized Phase 1, open-label, single-center, single-dose study is approximately 7 days, with a 30-day safety follow up. The maximum period of confinement is expected to be 14 days. The minimum period of confinement is expected to be 3 days. Inpatient stay must be extended until >90% radioactive dose administered has been recovered or <1% is excreted in total (urine and feces) in any 24H period for two consecutive days. Maximum confinement will be 14 days.

The expected duration of participation from Screening to the follow-up telephone contact will be approximately 5 weeks (minimum) to 8 weeks (maximum). Approximately 6 participants will be enrolled to study intervention.

On Day-1, participants will be admitted in order to ensure that a group of 6 participants are dosed on Day 1. The study will dose 6 adult male participants in order to ensure that at least 4 participants provide evaluable data. There are no plans to replace participants who are prematurely withdrawn.

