5.2. Exclusion Criteria

Participants are excluded from the study if any of the following criteria apply:

Medical Conditions:

1. Evidence or history of clinically significant hematological, renal, endocrine, pulmonary, gastrointestinal, cardiovascular, hepatic, psychiatric, neurological, or allergic disease (including drug allergies, but excluding untreated, asymptomatic, seasonal allergies at the time of dosing).
2. Any condition possibly affecting drug absorption (eg, gastrectomy, cholecystectomy, gastric bypass, duodenotomy, colectomy, history of inflammatory bowel disease).
3. History of HIV infection, hepatitis B, or hepatitis C; positive testing for HIV, HBsAg, or HCVA. Hepatitis B vaccination is allowed.
4. Participants with a history of irregular bowel movements; e.g., less than 1 bowel movement per day, regular episodes of diarrhea or constipation, irritable bowel syndrome (IBS) or lactose intolerance.
5. Other medical or psychiatric condition including recent (within the past year) or active suicidal ideation/behavior or laboratory abnormality or other conditions or situations related to COVID-19 pandemic (eg. Contact with positive case)] that may increase the risk of study participation or, in the investigator's judgment, make the participant inappropriate for the study.

Prior/Concomitant Therapy:

6. Use of prescription or nonprescription drugs and dietary and herbal supplements within 7 days or 5 half-lives (whichever is longer) prior to the first dose of study intervention with the exception of moderate/potent CYP3A inducers which are prohibited within 14 days plus 5 half-lives prior to the first dose of study intervention.. (Refer to Section [6.8 Concomitant Therapy](#) for additional details).
7. Current use of any prohibited concomitant medication(s) or those unwilling/unable to use a permitted concomitant medication(s). Refer to Section [6.8 Concomitant Therapy](#).

Prior/Concurrent Clinical Study Experience:

8. Previous administration with an investigational drug within 30 days (or as determined by the local requirement) or 5 half-lives preceding the first dose of study intervention used in this study (whichever is longer).

Diagnostic Assessments:

9. A positive urine drug test.

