5.3.1. Meals and Dietary Restrictions

- Participants must abstain from all food and drink (except water) at least 4 hours prior to any safety laboratory evaluations and 8 hours prior to the collection of the predose PK sample.
- Water is permitted until 1 hour prior to study intervention administration. Water may be consumed without restriction beginning 1 hour after dosing. Noncaffeinated drinks (except grapefruit or grapefruit-related citrus fruit juices—see below) may be consumed with meals and the evening snack.
- Lunch will be provided approximately 4 hours after dosing.
- Dinner will be provided approximately 9 to 10 hours after dosing.
- An evening snack may be permitted.

- Participants will refrain from consuming red wine, grapefruit, or grapefruit-related citrus fruits (eg, Seville oranges, pomelos) from 7 days prior to the first dose of study intervention until collection of the final PK blood sample.
- While participants are confined, their total daily nutritional composition should be approximately 55% carbohydrate, 30% fat, and 15% protein. The daily caloric intake per participant should not exceed approximately 3200 kcal.
- To help assure regularity in bowel movements, nutritional composition should contain at least 15 g of fiber per 1000 kcal or fiber capsules containing the equivalent amount of fiber may be administered daily (beginning at least 8 hr after dosing).

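### Low priority: the <1% discharge limb does not require a stool, so two stool-free days at 90% recovery or less can end collection with fecal radioactivity still unvoided

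*Protocol*

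**What the plan says.** Protocol 4.1 has two discharge limbs joined by an or: more than 90% of the radioactive dose recovered, or "<1% is excreted in total (urine and feces) in any 24H period for two consecutive days". The maximum stay is 14 days. SoA footnote a gives the same rule, opening "Inpatient stay must be extended until >90% radioactive dose administered has been recovered or <1% is excreted in total (urine and feces" and continuing as above. SAP 2.1 repeats it.

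Collection stops at discharge. Urine is taken at set intervals "and each subsequent 24H interval up to discharge", and feces "in intervals of each 24H period post dose up to discharge".

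Several provisions bear on the risk:

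- Section 5.2 excludes "Participants with a history of irregular bowel movements; e.g., less than 1 bowel movement per day".
- Section 5.3.1 says "nutritional composition should contain at least 15 g of fiber per 1000 kcal", or equivalent fiber capsules.
- Section 6.8 calls for more fluid and a mild laxative if there is no stool 36 to 48 h after the dose, aiming at a stool a day. Section 8.4.2.3 refers back to it.
- Section 8.4.3.1 stresses complete quantitative collection of all samples.
- SoA footnote c gives an approximate discharge time, "Procedures to be completed at time of discharge (approximately 144 hours post dose) only", and makes the discharge laboratory tests wait until the footnote a criteria are met. Section 4.1 gives an expected minimum confinement of 3 days.
- The Extent of Excretion set (Protocol Table 2, SAP 5.1.3) requires evaluable urinary and fecal data, without defining evaluable. It removes participants with deviations or AEs, such as severe constipation, that may have affected the analysis.

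**The concern.** The <1% limb is meant to show that excretion is essentially over. An interval without a stool contributes 0% feces to the sum, so on two such days the limb shows only that nothing was passed. The most exposed case is a gap late in the stay, because the only timed laxative trigger in 6.8 runs from the dose.

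The primary endpoint is cumulative urinary, fecal and total recovery as a percentage of dose. Stopping on two stool-free days biases that participant's fecal and total recovery low, and the sample cannot be obtained afterwards. If he is then judged not evaluable, one of 6 is lost, where at least 4 evaluable participants are wanted and none is replaced.

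**Working it through.** The plan states no figure to reproduce: N = 6 is said not to rest on empirical data or hypothesis testing. The check therefore applies the rule as written and then sizes the gap under stated assumptions.

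**1. Logic.** Let U and F be the percent of dose in urine and feces in one 24 h interval. The limb needs U + F < 1 in two consecutive intervals. With no stool F = 0, so it reduces to U < 1 in both. Bowel content does not enter. If cumulative recovery is above 90%, the other limb already applies and the gap is harmless.

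**2. Worked examples.** All inputs are assumptions. Urine is 30% of dose with t1/2 10 h. A fraction G reaches the bowel with half-life T. Stools are daily to 96 h, then none from 96 to 144 h.

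- Urine, 96–120 h: 30 × (2^(-9.6) − 2^(-12)) = 0.03%. Urine, 120–144 h: 30 × (2^(-12) − 2^(-14.4)) = 0.006%. Both are below 1%, so the limb is met.
- Held in the bowel at 144 h = G × (2^(-96/T) − 2^(-144/T)).
- G = 70%, T = 36 h: recovered at 96 h = 29.96 + 70 × (1 − 0.1575) = 88.9% (89.0% at 144 h). Held = 70 × (0.1575 − 0.0625) = 6.65%.
- G = 60%, T = 36 h: recovered 80.5%, held 60 × 0.0950 = 5.70%.
- G = 60%, T = 24 h: recovered 29.96 + 60 × (1 − 0.0625) = 86.2%, held 60 × (0.0625 − 0.0156) = 2.8%.
- G = 70%, T = 24 h: recovered at 96 h = 29.96 + 70 × 0.9375 = 95.6%. The >90% limb applies and this gap costs nothing.

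Shift in the mean of 6 for the two 36 h cases: 6.65/6 = 1.11 and 5.70/6 = 0.95 points. The median of 6 does not move if the other five are alike. Release after 144 h is not counted.

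**3. Frequency by hand.** Suppose each day has an independent chance q of no stool, over 4 days in which urine is already below 1%. The chance of a two-day stool-free run is p = 3q² − 2q³, and the chance for at least one of 6 is 1 − (1 − p)^6.

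- q = 0.05: p = 0.00725, giving 4.3%.
- q = 0.10: p = 0.028, giving 15.7%. Three or more of 6 affected, which would leave fewer than 4: 0.04%.

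**4. Simulation.** 100,000 participants per scenario: urine 20–30% of dose (t1/2 8–10 h), gut 60–70% (t1/2 24–36 h), daily stool probability 0.90–0.95, each stool emptying the pool, and at most 13 post-dose intervals (assumed from the 14-day maximum including Day -1). Laxative success, where used, applies from the second consecutive stool-free day. The result is the chance that at least one of 6 is stopped by the <1% limb with more than 2% of dose unvoided.

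| Setting | Chance |
|---|---|
| No discharge before 144 h, no laxative effect | about 0–16% |
| No discharge before 144 h, 80% laxative success | about 0–3% (upper end 3.4–3.6% in repeated runs) |
| Discharge allowed from 72 h, no laxative effect | up to about 24% |

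The risk depends strongly on the assumed total recovery. At stool probability 0.90 with the 144 h floor and no laxative effect, urine 30% with gut 65% (36 h) gives about 10.7%, and urine 25% with gut 67% (24 h) about 5.8%. A reachable 90% therefore does not remove the risk.

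**5. With one fecal sample required in the two intervals.** No scenario gave a stop with more than 2% unvoided. That also held when each stool emptied only 80% or 60% of the pool. If a stool carries less than 1% of dose and empties a fraction e, what remains is below 1% × (1 − e)/e, or 0.67% at e = 0.6, plus the next day's input. Much lower emptying was not tested.

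**The case against.** The strongest reply is that the plan already guards against this and that little is at stake. Participants with irregular bowels are excluded, fiber is supplied, and a daily stool is an explicit goal. Section 2.2.5 names "dizziness, headache, diarrhea, nausea and acne" as the commonest AEs in healthy subjects; constipation is not among them. Two untreated stool-free days would run against the conduct that 6.8 and 8.4.3.1 describe. The rule says the stay must be extended until a limb is met; it sets the earliest discharge and does not compel one, so an attentive site could keep the participant up to 14 days. There is no hypothesis test, totals are listed by participant and individual profiles are plotted, so a truncated curve would be seen.

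All of that stands and is why the point is low priority. It does not close the gap: the safeguards lower the chance without entering the criterion, and an analysis-set exclusion can drop a participant but cannot recover a sample.

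A reader might go further and infer that the plan disconnects everything else from the discharge rule. It does not: SoA footnote c refers expressly to the footnote a criteria and gives about 144 h. It simply adds no stool condition.

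**Conclusion.** The gap is real but small, and rated COULD. As written, the <1% limb can be met because nothing was passed, and the loss to the primary endpoint is then permanent for that participant. The logic follows from the text alone.

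The size rests on assumed excretion and stool frequencies: a tail risk of about 0 to 16% that any of the 6 is affected with a 144 h floor and no laxative effect, about 0 to 3% if laxatives work 80% of the time, and up to about 24% if discharge from 72 h is allowed without laxative effect. In the 36 h examples the loss is about 6 to 7% of dose, moves the mean of 6 by about 1 point, and would be visible in the individual listings.

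Two stronger readings are not supported. The documents do not show that recovery will be underestimated across the study; that would need stool-free runs in several participants, which the eligibility and bowel provisions work against. Nor do they show that the minimum of 4 evaluable participants is in danger: the hand calculation puts three or more affected at 0.04% even with a 10% daily chance of no stool.

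**What to change.** In Protocol 4.1, SoA footnote a and SAP 2.1, state that the <1% limb counts as met only if at least one fecal sample was obtained within the two consecutive 24 h intervals. Leave the >90% limb, the 14-day maximum and the laxative guidance unchanged. The clause governs only when sample collection may end.

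The cost is one clause in three places and a slightly longer stay for a few participants. With the 144 h floor and no laxative effect, the average added stay is at most about 0.04 day at stool probability 0.95 and 0.16 day at 0.90; without the floor it is up to about 0.3 day. If each stool empties only 60% of the pool, the average is up to 0.23 day, and up to 0.9% of participants reach the 14-day maximum with neither limb met.
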